### 3.2.1.2 Diagnostic Sensitivity of $^{68}\text{Ga}$ -OPS202 (For Phase 1 and Phase 2):

a) Diagnostic sensitivity of  $^{68}\text{Ga}$ -OPS202 imaging at baseline using RECIST as the SOT by subject-based analysis. The SOT is the results on RECIST from the contrast enhanced CT (or contrast enhanced MRI) scan images performed 6 weeks after second  $^{177}\text{Lu}$ -OPS201 administration (second cycle). Complete response (CR), partial response (PR) and stable disease (SD) will be considered as positive response, while progressive disease (PD) will be considered as negative response.

Diagnostic sensitivity between  $^{68}\text{Ga}$ -OPS202 at baseline and SOT will be assessed using performance specified in Table 7.

Table 7 Diagnostic performance of  $^{68}\text{Ga}$ -OPS202 PET/CT compared to RECIST as the SOT

$^{68}\text{Ga}$ -OPS202 PET/CT scan results	SOT results (using RECIST)	
	Positive (CR + PR + SD) 6 weeks post 2nd $^{177}\text{Lu}$ OPS201	Negative (PD) 6 weeks post 2nd $^{177}\text{Lu}$ OPS201
Subjects with lesions detected by $^{68}\text{Ga}$ -OPS202 at baseline	Positive Response	Negative Response

SAP Final: Version 2.0: [03 January 2020]

40/57

The sensitivity corresponds to the probability of positive response from  $^{177}\text{Lu}$ -OPS201 based on lesions identified with ceCT (or ceMRI). Sensitivity will be computed using following formula, for overall subjects (subject-based approach):

$$Sensitivity = \frac{Positive\ Response}{Positive\ Response + Negative\ Response}$$

For Phase 1 subjects only, the above analysis will be repeated using volumetric RECIST as SOT.

b) Diagnostic sensitivity of  $^{68}\text{Ga}$ -OPS202 imaging at baseline using mGa-RECIST as the SOT by subject-based analysis. The SOT is the results from mGa-RECIST from the contrast enhanced CT (or contrast enhanced MRI) scan images performed 6 weeks after second  $^{177}\text{Lu}$ -OPS201 administration (second cycle). Complete response (CR), partial response (PR) and stable disease (SD) will be considered as positive response, while progressive disease (PD) will be considered as negative response.

Diagnostic sensitivity between  $^{68}\text{Ga}$ -OPS202 at baseline and SOT will be assessed using performance specified in Table 8.

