## Phase II

The primary endpoint is ORR over the two treatment cycles of the core study. Objective response is defined using RECIST v1.1 measured by CT or magnetic resonance imaging (MRI). Tumour response assessments are performed 6 weeks after each administration of  $^{177}\text{Lu}$ -OPS201 during the core study or at the time of occurrence of first clinical signs of disease progression as determined by the investigator. Radiological interpretation for subject management will be performed at the site, whereas efficacy evaluation will be conducted by the ICL.

Primary and secondary tumour activity endpoints and evaluations are summarised in Table 2.

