- Subject has not sufficiently recovered from an adverse event despite extension of the dosing interval by 4 weeks (such as delayed grade 3-4 haematotoxicity)
- Hypersensitivity to the active substance or to any of the excipients of the study drugs
- Radiological disease progression

All cases of discontinuation will be discussed between the investigator and the sponsor.

A subject can also withdraw their consent to the treatment period but agree to take part in 24-month follow-up period.

If a subject is considered Not Evaluable for DLT due to withdrawal during DLT assessment period, he/she will be replaced by another subject.

In phase I, a cohort will be considered as completed once three subjects of the cohort complete Cycle 2 or discontinue early during Cycle 2. If subjects discontinue for any reason other than a DLT (e.g. disease progression) before end of Cycle 2, they might be replaced.

The phase I will be terminated once the MTCA has been determined. The phase II is designed with early stopping criteria, allowing any cohort to be closed early in case of futility.

A specific site or a given cohort can also be discontinued or the entire study may be terminated at any time if the sponsor judges it necessary for any reason. In that case, all scheduled procedures and assessments for subjects who are still in the study will be performed. Some possible reasons for the closure of a study site may include:

- failure of the investigator staff to comply with the protocol or with the Good Clinical Practice (GCP) guidelines.
- safety concerns.
- inadequate subject recruitment.

In case of premature discontinuation of a site or the complete study, depending on the reason(s) for the discontinuation, the sponsor will notify the investigator(s) affected in writing as to whether the ongoing subjects should continue the remaining IRPP dose administration(s).

Should, at the start of the study, 20 consecutive subjects fail screening due to Ga-OPS202 PET/CT negative for sstr2 with all the other inclusion/criteria met, the administration of Ga-OPS202 and subsequent PET imaging will be stopped. Selection of sstr2-positive tumours for the treatment with Lu-OPS201 will be revised in a protocol amendment.

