### 2.2.4 *$^{68}\text{Ga}$ -OPS202 response evaluable population*

All subjects in the  $^{68}\text{Ga}$ -OPS202 positive population with the following 6 weeks post second  $^{177}\text{Lu}$ -OPS201 administration (second cycle): a readable  $^{68}\text{Ga}$ -OPS202 PET, a readable ceCT scan, and a readable  $^{18}\text{F}$ -FDG-PET scan.

The  $^{68}\text{Ga}$ -OPS202 positive and  $^{68}\text{Ga}$ -OPS202 response evaluable populations will be used for the analyses of diagnostic endpoints of  $^{68}\text{Ga}$ -OPS202.

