### **3.2.4 Missing data and outliers**

#### **3.2.4.1 Missing data**

Missing data will not be imputed. Only observed data will be used in the summaries and analyses.

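### The RECIST-based diagnostic ratios use only subjects scanned after the second dose, so early failures drop out and the disease-control proportion is biased upward

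*SAP*

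**What the plan says.** All references are to the SAP.

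- **Standard of truth.** Section 3.2.1.2 (a): "The SOT is the results on RECIST from the contrast enhanced CT (or contrast enhanced MRI) scan images performed 6 weeks after second" 177Lu-OPS201 administration. Section 3.2.1.2 (b): "The SOT is the results from mGa-RECIST from the contrast enhanced CT (or contrast enhanced MRI) scan images performed 6 weeks after second" 177Lu-OPS201 administration. Both outcome columns of Tables 7 and 8 carry that timepoint.
- **Cells.** CR, PR and SD are positive; "progressive disease (PD) will be considered as negative response". The tables have one row, subjects with lesions detected by 68Ga-OPS202 at baseline.
- **Interpretation.** "The sensitivity corresponds to the probability of positive response from" 177Lu-OPS201.
- **Earlier scan.** Section 1.3.2.1, Phase II: "Tumour response assessments are performed 6 weeks after each administration of" 177Lu-OPS201. Tables 1 and 2 give the same RECIST v1.1 timing for both phases.
- **Stopping.** Section 1.3.2.10 lists "Radiological disease progression" among the events after which no further treatment is given.
- **Analysis set.** Section 2.2.4 requires readable 68Ga-OPS202 PET, ceCT and FDG-PET scans 6 weeks after the second administration.
- **Missing data.** Section 3.2.4.1 does not impute: "Only observed data will be used in the summaries and analyses".
- **Status.** Section 3.1.2 lists both ratios as secondary endpoints in both phases.

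**The concern.** The ratio is described as a probability of benefit in subjects with a positive baseline scan, but its denominator is decided by what happens after treatment starts. A subject must stay free of acted-on progression, and alive, long enough to receive a second dose and be scanned 6 weeks later. Those who fail sooner are treatment failures, yet they are not in the negative cell; they are absent. This is a different matter from requiring a positive baseline scan, which selects on a pre-treatment feature.

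The SAP handles the same subjects differently elsewhere. The phase II PP population (2.2.2) needs only one post-baseline assessment, so a subject who progresses at the Cycle 1 scan can enter the ORR denominator as a non-responder. Table 4 counts that progression as a PFS event. One subject can thus be a failure for ORR and PFS and missing from the ratio in 3.2.1.2. What is at stake is a secondary endpoint that would overstate disease control in treated positive subjects.

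**Working it through.** The SAP gives no value, target or sample size for these two ratios, so there is no stated figure to reproduce.

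**Step 1: does an early failure reach either cell?**
1. Progression acted on at the Cycle 1 scan means no second administration (1.3.2.10), hence no scan 6 weeks after it. Death before that scan has the same result.
2. Tables 7 and 8 have no cell for such a subject.
3. The response evaluable population (2.2.4) excludes the subject. The 68Ga-OPS202 positive population (2.2.3), also named for diagnostic endpoints, does not help, because the cells themselves need the later result.
4. Section 3.2.4.1 does not impute. The carry-forward rule in Appendix 1 (16) applies only when a later assessment exists and shows no progression.

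So, as a rule, the subject is dropped.

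**Step 2: direction.** Let P be subjects with CR, PR or SD at the later scan, Q those with PD at it, and E those with PD or death before it.

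- Planned ratio = P/(P + Q)
- Ratio counting early failures = P/(P + Q + E)
- With e = E/(P + Q + E), the second ratio = (1 − e) × the planned ratio
- Overstatement = e × the planned ratio

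This is above zero whenever E and P are both at least 1. The direction needs no assumed rate.

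**Step 3: size.** Neither e nor the PD share at the later scan (d) is in the SAP; both are assumptions here. The planned ratio is 1 − d, so the overstatement is e × (1 − d). In percentage points:

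| e | d = 20% | d = 30% | d = 40% |
|---|---|---|---|
| 5% | 4.0 | 3.5 | 3.0 |
| 10% | 8.0 | 7.0 | 6.0 |
| 20% | 16.0 | 14.0 | 12.0 |
| 30% | 24.0 | 21.0 | 18.0 |

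**Step 4: check with whole subjects.** As illustrative denominators, take 30 (the phase I maximum), 69 and 87 (the phase II response-evaluable numbers). With 69 subjects and d = 30%:

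| e | E | P | Q | Planned P/(P + Q) | Early failures counted, P/69 |
|---|---|---|---|---|---|
| 5% | 3 | 46 | 20 | 0.697 | 0.667 |
| 10% | 7 | 43 | 19 | 0.694 | 0.623 |
| 20% | 14 | 39 | 16 | 0.709 | 0.565 |
| 30% | 21 | 34 | 14 | 0.708 | 0.493 |

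The planned ratio stays near 0.70 while the other falls to about 0.49. Across the three denominators and d = 20% to 40%, the gap is about 3–5 points at e = 5%, 6–8 at 10%, 12–16 at 20% and 18–24 at 30%. The 5 at the low end is rounding: 5% of 30 becomes 2 subjects (6.7%), and with d = 20% this gives 22/28 = 0.786 against 22/30 = 0.733.

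**The case against.** **The ratio may never be produced.** Section 5 revises the study report after premature closure and selects listings of disposition, deviations, demographics, imaging-product administration and adverse events. No tumour-response or diagnostic-sensitivity output is among them. A reader might infer that an inflated figure will appear in the report; the document does not support that. This stands and lowers the urgency. Section 3.2.1.2 nevertheless remains in the SAP with the faulty rule.

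**The ratio does not measure prediction.** A reader might infer that the tracer is made to look more predictive than it is. That goes too far. Tables 7 and 8 have no scan-negative row, so the ratio cannot show predictiveness with or without early failures. The related objectives in 1.1.2 concern uptake and tumour response, and separate correlation analyses in 3.2.1.1 address those. What is biased is a disease-control proportion.

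**The exclusion is not absolute.** A reader might infer that no early progressor can ever be counted. Section 1.3.2.1 has sites read scans for management and the imaging core laboratory (ICL) read them for efficacy. Progression called only by the ICL need not stop treatment, so that subject may reach the later scan.

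**Early progressors are visible elsewhere.** BOR and DCR are summarised in 3.2.1.1, in phase II on the ITT population as well as the PP population. This is a partial safeguard. DCR uses best response, so a subject stable at the first scan and progressing at the second is controlled for DCR but negative in Table 7.

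**The size is assumed.** This is correct, and at low e it is modest.

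**Conclusion.** The point holds as a defect in the definition of a secondary endpoint. As written, analyses (a) and (b) as a rule leave out treated 68Ga-OPS202-positive subjects who progress or die before the scan 6 weeks after the second administration. Read as disease-control proportions in that group, the ratios are biased upward by a factor 1/(1 − e).

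The direction follows from the SAP's text. The size does not: it runs from about 3 points at e = 5% to about 24 points at e = 30%, with 20% to 40% progression assumed at the later scan. The formula covers only subjects who either reach that scan or fail before it; those who stop for other reasons are outside it. Given section 5, the practical effect is confined to the analysis being run after all or its definition being reused.

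**What to change.** **Analysis (a), Table 7.** Use all treated 68Ga-OPS202-positive subjects, in place of the section 2.2.4 requirement for scans after the second administration.

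- Negative: RECIST v1.1 PD or death at any time up to and including the scan 6 weeks after the second administration.
- Positive: CR, PR or SD at that scan.
- Neither that scan nor earlier PD or death (for example toxicity, an organ-dose limit or withdrawal): report the number with reasons, and show the ratio with these subjects excluded and with them counted as negative.

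**Analysis (b), Table 8.** Keep the ratio as defined, because mGa-RECIST is restricted to lesions avid at baseline and has no Cycle 1 read. State how many subjects lack the read because of earlier RECIST v1.1 PD or death. Add a sensitivity analysis counting them as negative, noting that such PD may lie in non-avid lesions.

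**Cost.** SAP wording and slightly more analysis; the Cycle 1 RECIST reads and deaths are already collected. The figure will be lower wherever early failures occur. The treatment-stopping rule is not questioned.

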**Table 8 Diagnostic performance of  $^{68}\text{Ga}$ -OPS202 PET/CT compared to mGa-RECIST\* as the SOT**

$^{68}\text{Ga}$ -OPS202 PET/CT scan results	SOT results (using mGa-RECIST)	
	Positive (CR + PR + SD) 6 weeks post 2nd $^{177}\text{Lu}$ OPS201	Negative (PD) 6 weeks post 2nd $^{177}\text{Lu}$ OPS201
Subjects with lesions detected by $^{68}\text{Ga}$ -OPS202 PET/CT at baseline	Positive Response	Negative Response

\*modified Ga-RECIST using RECIST criteria on only those lesions which are  $^{68}\text{Ga}$ -OPS202 avid at baseline

The sensitivity corresponds to the probability of positive response from  $^{177}\text{Lu}$ -OPS201 based on lesions identified with  $^{68}\text{Ga}$ -OPS202-PET/ceCT (or ceMRI). Sensitivity will be computed using following formula, for overall subjects (subject-based approach):

$$Sensitivity = \frac{Positive\ Response}{Positive\ Response + Negative\ Response}$$

For Phase 1 subjects only, the above analysis will be repeated using volumetric mGa-RECIST as SOT.

c) Diagnostic sensitivity of  $^{68}\text{Ga}$ -OPS202 imaging at baseline by subject-based, organ-based and lesion-based analysis compared to standard-of-truth (SOT). The SOT is the contrast enhanced CT (or contrast enhanced MRI) scan images acquired at baseline.

Diagnostic sensitivity between  $^{68}\text{Ga}$ -OPS202 at baseline and SOT at baseline will be assessed using performance specified in Table 9.

**Table 9 Diagnostic performance of  $^{68}\text{Ga}$ -OPS202 PET/CT compared to SOT of ceCT (or ceMRI)**

$^{68}\text{Ga}$ -OPS202 PET/CT scan results	SOT results (ceCT/ceMRI)	
	Lesions detected at baseline	Lesions not detected at baseline
Lesions detected at baseline	True Positive (TP)	False Positive (FP)
Lesions not detected at baseline	False Negative (FN)	True Negative (TN)* [will remain unknown]

\*True negative will remain unknown at the lesion level

The sensitivity corresponds to the probability that the  $^{68}\text{Ga}$ -OPS202 scan at baseline detects the lesions, given that the lesions are detected (positive) by SOT at baseline. This measurement refers to the ability of the test to correctly identify those lesions with the outcome of interest. Sensitivity is defined as the proportion of lesions with a positive ‘standard’ test response who also have a positive ‘experimental’ test response.

For each assessment, the sensitivity will be computed using following formula, for each subject, for each organ and overall lesions:

$$\text{Sensitivity} = \frac{TP}{TP + FN}$$

d) Diagnostic sensitivity of  $^{68}\text{Ga}$ -OPS202 imaging at baseline by both organ-based and lesion-based analysis compared to the SOT of  $^{177}\text{Lu}$ -OPS201 SPECT/CT after first administration. The contrast enhanced CT (or contrast enhanced MRI) scan images acquired at baseline will be used for anatomical location and lesion mapping between the two imaging techniques.

Diagnostic sensitivity between  $^{68}\text{Ga}$ -OPS202 at baseline and  $^{177}\text{Lu}$ -OPS201 SPECT/CT as SOT will be assessed using performance specified in Table 10.

**Table 10 Diagnostic performance of  $^{68}\text{Ga}$ -OPS202 compared to SOT of  $^{177}\text{Lu}$ -OPS201 SPECT/CT**

$^{68}\text{Ga}$ -OPS202 scan results	SOT results ( $^{177}\text{Lu}$ -OPS201 SPECT/CT)	
	Lesions detected after first administration of $^{177}\text{Lu}$ -OPS201	Lesions not detected after first administration of $^{177}\text{Lu}$ -OPS201
Lesions detected at baseline	True Positive (TP)	False Positive (FP)
Lesions not detected at baseline	False Negative (FN)	True Negative (TN) [will remain unknown]*

\*True negative will remain unknown at the lesion level

The sensitivity corresponds to the probability that the  $^{68}\text{Ga}$ -OPS202 detects the lesion identified on the  $^{177}\text{Lu}$ -OPS201 SPECT/CT scan after first administration. This measurement refers to the ability of the test to correctly identify those lesions with the outcome of interest. Sensitivity is defined as the proportion of lesions with a positive ‘standard’ test response who also have a positive ‘experimental’ test response.

For each assessment, the sensitivity will be computed using following formula, for each organ and overall lesions:

$$\text{Sensitivity} = \frac{TP}{TP + FN}$$

### 3.2.2 Safety

All safety data will be included in the data listings and summary tables will be based on the safety population.

For phase I study, continued monitoring of DLTs and toxicities will be performed. At the time of each data review board (DRB), the available safety data, including DLTs, toxicities, physiological parameters, ECG, laboratory test results and selected organ absorbed radiation doses (kidney and BM) will be tabulated to guide the radioactivity selection during the dose escalation.

For the overall study, descriptive statistics will be calculated for the safety parameters. No formal statistical analyses of safety data are planned.

Summaries will be prepared by cohort and, as needed, by timepoint.

The NCI-CTCAE version 5.0 classification will be used to classify all TEAEs and laboratory abnormalities.

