### **1.2.1 Study population**

This study will be conducted at approximately 30 global clinical sites. Eight of these sites will participate in phase I and all sites in phase II. Participating regions are planned to be North America, Europe and Asia-Pacific. Additional sites may be added.

During phase I, up to 30 subjects will be enrolled for treatment with  $^{177}\text{Lu}$ -OPS201. Based on the current knowledge on the proportion of subjects presenting with sstr2-positive tumours, it is anticipated that approximately 55 to 60 subjects will need to be administered  $^{68}\text{Ga}$ -OPS202. Should, at the start of the study, 20 consecutive subjects fail screening due to  $^{68}\text{Ga}$ -OPS202 PET/CT negative for sstr2 with all the other inclusion/criteria met, the administration of  $^{68}\text{Ga}$ -OPS202 and subsequent PET imaging will be stopped. Selection of sstr2-positive tumours for the treatment with  $^{177}\text{Lu}$ -OPS201 will be revised in a protocol amendment.

During phase II, approximately 172 subjects (76 subjects with SCLC and 96 with BC) are planned to be enrolled for the Simon's optimal two-stage design. In this study phase, it is anticipated that approximately 340 subjects will need to be administered  $^{68}\text{Ga}$ -OPS202 for PET imaging screening. However, recruitment will be stopped once the number of required evaluable subjects (i.e. 76 subjects with SCLC and 96 with BC) is reached.

Further cohorts of subjects with other tumours expressing sstr2 could be added in this protocol according to the advances in the preclinical and clinical knowledge on  $^{68}\text{Ga}$ -OPS202 and  $^{177}\text{Lu}$ -OPS201 and emerging published data on the diseases. In this case, the additional number of subjects will be estimated based on standard of care historical response (e.g. ORR/best overall response (BOR)) of the corresponding disease.

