## 2.3 Safety

Safety population is all subjects who received at least one dose of  $^{177}\text{Lu}$ -OPS201 or  $^{68}\text{Ga}$ -OPS202.

- $^{68}\text{Ga}$ -OPS202 safety population: All subjects who received at least one dose of  $^{68}\text{Ga}$ -OPS202.
- $^{177}\text{Lu}$ -OPS201 safety population: All subjects who received at least one dose of  $^{177}\text{Lu}$ -OPS201.

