## 2.7 Primary population

For the phase I of the study, the primary analysis based on the primary safety endpoint will be performed on the MTCA evaluable population.

For the phase II of the study, the primary analysis based on the primary efficacy endpoint will be performed on the PP population. In addition, secondary/confirmatory analysis may be performed on the ITT population.

The primary dosimetry analysis will be based on the dosimetry population. A supportive analysis will be based on per protocol dosimetry population.

The assessment of safety and tolerability will be based on the safety population.

The assessment of PK will be based on the radiopharmaceutical pharmacokinetic population and OPS201 pharmacokinetic population.

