### **3.2.14 *Rules and data formats***

Data will be presented using an appropriate number of decimal places (i.e. the number of decimal places used does not imply undue precision). Raw data will be presented to the number of decimal places collected, and derived data will be presented to an appropriate number of decimal places. The appropriate number of decimal places will be determined by general practice, mathematical rationale or scientific rationale (e.g. age should be presented in whole numbers).

For summary statistics, the following will be presented n, number of missing values, arithmetic mean, standard deviation, median and the range (minimum, maximum).

Mean, median, standard deviation and standard errors of the mean (SE) values will be reported to one decimal place greater than the raw/derived data that they summarise. Minimum and maximum values will be reported with the same precision as the raw data.

Percentages will be reported to one decimal place and 0% will not be presented. Percentages will be calculated using a denominator of all subjects in a specified population. The denominator will be specified in a footnote to the tables for clarification if necessary.

Lower and upper confidence interval values should be presented to one decimal place more than the raw/derived data (i.e., to the same number of decimal places as the mean).

Percentiles (e.g., 25% or first quartile, 75% third quartile) should be presented to one decimal place more than the raw/derived data.

P-values will be reported to four decimal places (e.g.: p=0.0037), after rounding. P-values which are less than 0.0001 will be presented as '<0.0001'.

All values below or above a limit of detection (e.g. <0.1 or >100) will be listed as such.

All text fields must be left justified and numeric or numeric with some text specification must be decimal justified. Dates will be presented in the format [ddmmmyyyy] and times in the format [hh:mm].

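### Safety tables use a safety population that includes subjects given only 68Ga-OPS202, which would roughly halve 177Lu-OPS201 TEAE percentages in the Phase I total and Phase II overall columns

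*SAP*

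**What the plan says.** Section 2.3 opens with a union definition: "Safety population is all subjects who received at least one dose of" either 177Lu-OPS201 or 68Ga-OPS202. Beneath it the section defines two product-specific sets, one for the tracer and one for the therapy ("OPS201 safety population: All subjects who received at least one dose of" 177Lu-OPS201). Neither is assigned to an analysis anywhere in the SAP.

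The two places that choose a population for safety name the union without a product qualifier. Section 2.7: "The assessment of safety and tolerability will be based on the safety population". Section 3.2.2: "All safety data will be included in the data listings and summary tables will be based on the safety population". Section 3.2.14 then fixes the denominator: "Percentages will be calculated using a denominator of all subjects in a specified population".

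Section 3.2.2.1 defines a general TEAE relative to the first 177Lu-OPS201 administration. It gives 68Ga-OPS202 TEAEs a separate definition, with a window ending one day after the tracer. Section 3.1 asks for Phase I results by cohort and in total, and for Phase II safety results by cancer type and in total.

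**The concern.** A subject who has the tracer at screening and is then found ineligible never receives 177Lu-OPS201. That subject cannot have an event that is treatment-emergent relative to the therapy, yet belongs to the safety population and so to the denominator. The affected rows of the overall adverse event table are the 177Lu-OPS201 TEAE rows, including grade 3 to 5 events, serious events, discontinuations and DLTs. The tables by system organ class and preferred term are affected in the same way.

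By the plan's own expectations, such subjects are close to half of everyone given the tracer. The therapy's toxicity would look about half as frequent as it was among the subjects who received it. Other analysis sets in section 2 are tied explicitly to their uses (PP, the diagnostic sets, MTCA evaluable, dosimetry, PK), so the missing assignment of the two safety subsets looks like an oversight.

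**Working it through.** **Inputs**
- Phase I treated, section 1.2.1: "During phase I, up to 30 subjects will be enrolled for treatment with" 177Lu-OPS201, so 30 at most.
- Phase I tracer-dosed, section 1.2.1: "it is anticipated that approximately 55 to 60 subjects will need to be administered" 68Ga-OPS202.
- Phase II treated, section 1.2.1: 172, made up of 76 SCLC and 96 BC.
- Phase II tracer-dosed, section 1.2.1: "it is anticipated that approximately 340 subjects will need to be administered" 68Ga-OPS202.

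**The plan's own figure.** Section 1.3.4 takes 69 and 87 evaluable subjects with a 10% allowance: 69 × 1.10 = 75.9, rounded to 76; 87 × 1.10 = 95.7, rounded to 96; 76 + 96 = 172. The stated total is reproduced. The 55 to 60 and the 340 are stated anticipations with no underlying sstr2-positive rate, so they are taken as given.

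**Size of the union.** Section 1.2 (pre-treatment period) has every treated subject imaged with 68Ga-OPS202 first. The number given either product therefore equals the number given the tracer.

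**Dilution factor** = treated ÷ safety population.

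| Column | Factor |
|---|---|
| Phase I total | 30/60 = 0.50 to 30/55 = 0.55 |
| Phase II overall | 172/340 = 0.51 |
| Phase I cohort column | about 1.0 |

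The last row follows from section 1.3.1: subjects are allocated to a cohort only once eligibility for treatment is confirmed, so tracer-only subjects have no cohort.

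**Effect on a printed percentage** = rate among treated × factor. The rates are illustrative; the plan states none.

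| Rate among treated | Phase I total prints | Phase II overall prints |
|---|---|---|
| 10% | 5.0 to 5.5% | 5.1% |
| 20% | 10.0 to 10.9% | 10.1% |
| 30% | 15.0 to 16.4% | 15.2% |

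**Phase II by cancer type.** Tracer-only subjects have a cancer type, so they can fall into these columns. The plan does not split the 340 − 172 = 168 of them. At the extremes, with all 168 in one cohort, the SCLC factor would be 76/(76 + 168) = 0.31 or 1.00, and the BC factor 96/(96 + 168) = 0.36 or 1.00. The factor within each type is unknown.

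**With the 177Lu-OPS201 safety population as denominator** (30 and 172), the factor is 1.00 in every column.

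**The case against.** The strongest reply is that nothing in the current report can be diluted. Section 5 says the study closed prematurely and selects data listings only; where these name a population, it is the eligibility screened one. No percentage table is among them. This stands and limits the practical effect. It does not correct sections 2.7 and 3.2.2, which remain the stated method in the final SAP and would govern any summary table that was run.

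A second reply is that the right sets exist in section 2.3, that section 3.1 speaks of the population that applies, and that section 3.2.14 allows a denominator footnote. A sensible programmer might therefore choose the 177Lu-OPS201 set. But for safety the population that the SAP names is the union, in two places, and a footnote discloses a denominator without changing it.

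Three stronger readings are tempting, and the document does not support them:
- A reader might infer that every adverse event rate is halved. Phase I cohort columns hold only subjects allocated for treatment. Tracer-only subjects can contribute 68Ga-OPS202 TEAEs, for which they properly belong in the denominator. Means of laboratory, vital sign and ECG values use observed data without imputation (section 3.2.4.1), so subjects with no on-treatment value do not dilute them; only frequency percentages are exposed.
- A reader might infer that the Phase I primary safety conclusion is at risk. Sections 2.4 and 2.7 put the MTCA determination on the MTCA evaluable population, all of whom received 177Lu-OPS201.
- A reader might infer that the final report will print halved rates. Section 5 rules that out for the outputs it selects.

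**Conclusion.** The concern holds within limits. The SAP names a denominator that does not match the events being counted, and the sets that would match are defined but unused. Followed as written, percentages of subjects with 177Lu-OPS201 TEAEs would be roughly halved in the Phase I total column and in Phase II overall. Phase II cancer-type columns are exposed too, by an amount that cannot be calculated from the plan.

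The sizes assume that the planned counts are met, that every enrolled subject is dosed and had the tracer first, and that tracer-only subjects contribute no 177Lu-OPS201 events. With a listings-only report this is worth correcting because the correction is nearly free and the text may be used again, not because a reported result is known to be wrong.

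**What to change.** In sections 2.7 and 3.2.2, replace the unqualified reference with three assignments:
- 177Lu-OPS201 TEAE summaries, including the grade 3 to 5, serious event, discontinuation and DLT rows, and on-treatment frequency tables for laboratory, vital sign, ECG and physical examination data use the 177Lu-OPS201 safety population.
- 68Ga-OPS202 TEAE summaries use the 68Ga-OPS202 safety population.
- The union set is used for listings.

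No new population or data are needed, and neither the MTCA analysis nor the Section 5 listings change. The cost is a few sentences of SAP text and the population labels and denominators in the table shells.
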